8.4.2.1. Exposure During Pregnancy (EDP)

For both unapproved/unlicensed products and for marketed products, an EDP occurs if:

- A female becomes, or is found to be, pregnant either while receiving or having been exposed (eg, because of treatment or environmental exposure) to the investigational product; or the female becomes or is found to be pregnant after discontinuing and/or being exposed to the investigational product.
- An example of environmental exposure would be a case involving direct contact with a Pfizer product in a pregnant woman (eg, a nurse reports that she is pregnant and has been exposed to chemotherapeutic products).
- A male has been exposed (eg, because of treatment or environmental exposure) to the investigational product prior to or around the time of conception and/or is exposed during his partner's pregnancy.

If a patient or patient's partner becomes or is found to be pregnant during the patient's treatment with the investigational product, the investigator must report this information to Pfizer Safety on the CT SAE Report Form and an EDP supplemental form, regardless of whether an SAE has occurred. In addition, the investigator must submit information regarding environmental exposure to a Pfizer product in a pregnant woman (eg, a patient reports that she is pregnant and has been exposed to a cytotoxic product by inhalation or spillage) to Pfizer Safety using the EDP supplemental form. This must be done irrespective of whether an AE has occurred and within 24 hours of awareness of the exposure. The information submitted should include the anticipated date of delivery (see below for information related to termination of pregnancy).

Follow-up is conducted to obtain general information on the pregnancy and its outcome for all EDP reports with an unknown outcome. The investigator will follow the pregnancy until completion (or until pregnancy termination) and notify Pfizer Safety of the outcome as a follow-up to the initial EDP supplemental form. In the case of a live birth, the structural integrity of the neonate can be assessed at the time of birth. In the event of a termination, the reason(s) for termination should be specified and, if clinically possible, the structural integrity of the terminated fetus should be assessed by gross visual inspection (unless

pre-procedure test findings are conclusive for a congenital anomaly and the findings are reported).

If the outcome of the pregnancy meets the criteria for an SAE [ie, ectopic pregnancy, spontaneous abortion, intrauterine fetal demise, neonatal death, or congenital (anomaly in a live-born baby, a terminated fetus, an intrauterine fetal demise, or a neonatal death)], then the investigator should follow the procedures for reporting SAEs.

Additional information about pregnancy outcomes that are reported to Pfizer Safety as SAEs follows:

- Spontaneous abortion includes miscarriage and missed abortion;
- Neonatal deaths that occur within 1 month of birth should be reported, without regard to causality, as SAEs. In addition, infant deaths after 1 month should be reported as SAEs when the investigator assesses the infant death as related or possibly related to exposure to the investigational product.

Additional information regarding the EDP may be requested by the sponsor. Further follow-up of birth outcomes will be handled on a case-by-case basis (eg, follow-up on preterm infants to identify developmental delays). In the case of paternal exposure, the investigator will provide the patient with the Pregnant Partner Release of Information Form to deliver to his partner. The investigator must document in the source documents that the patient was given the Pregnant Partner Release of Information Form to provide to his partner.

8.4.2.2. Exposure During Breastfeeding

Scenarios of exposure during breastfeeding must be reported, irrespective of the presence of an associated SAE, to Pfizer Safety within 24 hours of the investigator's awareness, using the CT SAE Report Form. An exposure during breastfeeding report is not created when a Pfizer drug specifically approved for use in breastfeeding women (eg, vitamins) is administered in accord with authorized use. However, if the infant experiences an SAE associated with such a drug's administration, the SAE is reported together with the exposure during breastfeeding.

8.4.2.3. Occupational Exposure

An occupational exposure occurs when, during the performance of job duties, a person (whether a healthcare professional or otherwise) gets in unplanned direct contact with the product, which may or may not lead to the occurrence of an AE.

An occupational exposure is reported to Pfizer Safety within 24 hours of the investigator's awareness, using the CT SAE Report Form, regardless of whether there is an associated SAE. Since the information does not pertain to a patient enrolled in the study, the information is not recorded on a CRF; however, a copy of the completed CT SAE Report Form is maintained in the investigator site file.

8.4.3. Medication Errors

Other exposures to the investigational product under study may occur in clinical trial settings, such as medication errors.

Safety Event	Recorded on the CRF	Reported on the CT SAE Report Form to Pfizer Safety Within 24 Hours of Awareness
Medication errors	All (regardless of whether associated with an AE)	Only if associated with an SAE

8.4.3.1. Medication Errors Definition

Medication errors may result from the administration or consumption of the investigational product by the wrong patient, or at the wrong time, or at the wrong dosage strength.

Medication errors include:

- Medication errors involving patient exposure to the investigational product;
- Potential medication errors or uses outside of what is foreseen in the protocol that do or do not involve the participating patient.

Such medication errors occurring to a study patient are to be captured on the medication error page of the CRF, which is a specific version of the AE page.

In the event of medication dosing error, the sponsor should be notified within 24 hours.

Whether or not the medication error is accompanied by an AE, as determined by the investigator, the medication error is recorded on the medication error page of the CRF and, if applicable, any associated AE(s), serious and non-serious, are recorded on an AE page of the CRF.

Medication errors should be reported to Pfizer Safety within 24 hours on a CT SAE Report Form **only when associated with an SAE**.

9. DATA ANALYSIS/STATISTICAL METHODS

Detailed methodology for summary and statistical analyses of the data collected in this study is outlined here and further detailed in a statistical analysis plan (SAP), which will be maintained by the sponsor. The SAP may modify what is outlined in the protocol where appropriate; however, any major modifications of the primary endpoint definitions or their analyses will also be reflected in a protocol amendment.

9.1. Analysis Sets

1. Safety analysis set.

The safety analysis set includes all enrolled patients who receive at least one dose of study treatment.

2. Full analysis set.

The full analysis set includes all enrolled patients.

3. Per protocol analysis set (evaluable for MTD).

The per-protocol analysis set includes all enrolled patients who receive at least one dose of study treatment and who do not have major treatment deviations during the first cycle. Patients with major treatment deviations during the first cycle of treatment are not evaluable for the MTD assessment and will be replaced as needed to permit the MTD estimation. Major treatment deviations include the failure to satisfy major entry criteria (eg, confirmation of the target disease; signed informed consent) or use of other anticancer treatments during the active treatment period and disease follow-up phases other than as defined/allowed in this protocol. Major treatment deviations will also include:

- Administration of less than 70% of the planned number of doses of PF-06952229 (provided that the reduction in doses is not due to toxicity attributable to PF-06952229).
- Administration of more than 110% of the planned number of doses of PF-06952229.
- 4. Modified Intent to Treat (mITT) Population.

The modified intent to treat (mITT) is the analysis population that will follow the ITT principle and include patients receiving at least 1 dose of investigational product with baseline assessment and at least 1 post baseline assessment, disease progression, or death before the first tumor assessment. The mITT population will be used for analyses and to support conference presentations when the study is still ongoing.

5. PK analysis sets.

The PK parameter analysis population is defined as all enrolled patients treated who have sufficient information to estimate at least 1 of the PK parameters of interest. The PK concentration population is defined as all enrolled patients who are treated and have at least 1 analyte concentration.

9.2. Statistical Methods and Properties

9.2.1. Statistical Methods for Dose Escalation

This study contains 2 parts, dose escalation with PF-06952229 (Part 1A), followed by dose escalation for PF-06952229 in combination with enzalutamide (Part 1B), and dose expansion for PF-06952229 as a monotherapy (Part 2A) and combination dose expansion of PF-06952229 with enzalutamide in patients with mCRPC (Part 2B).

Part 1A Single Agent PF-06952229 and Part 1B PF-06952229 Plus Enzalutamide Combination Dose Escalation

The dose escalation in Part 1A will start with Accelerated Titration Design (ATD) as proposed by Simon et al (Journal of the National Cancer Institute, Vol. 89, No. 15, August 6, 1997). Part 1 will have an initial accelerated phase followed by a standard (mTPI) escalation phase. During the accelerated phase, initial cohorts to contain a minimum of one patient until the first instance of first-cycle CTCAE grade ≥2 toxicity.

The traditional mTPI design⁴ uses a Bayesian statistics framework and a beta/binomial hierarchical model to compute the posterior probability of 3 dosing intervals that reflect the relative difference between the toxicity rate of each dose level to the target rate (pT = 0.275). If the toxicity rate of the currently used dose level is far smaller than pT, the mTPI will recommend escalating the dose level; if it is close to target probability (pT), the mTPI will recommend continuing at the current dose; if it is far greater than pT, the mTPI will recommend de-escalating the dose level. These rules are conceptually similar to those used by the 3+3 design, except the decisions of an mTPI design are based on posterior probabilities calculated under a coherent probability model. The proposed mTPI method for this protocol includes stopping rules and dose escalation criteria, which prevents the target DLT rate to reach \geq 33% for determining the MTD. This proposed mTPI method is more conservative than the traditional TPI method.

Decision rules are based on calculating unit probability mass (UPM) of 3 dosing intervals corresponding to under, proper, and over dosing in terms of toxicity. Specifically, the underdosing interval is defined as (0; pT-e1), the over-dosing interval (pT+e2, 1), and the proper-dosing interval (pT- e1, pT+ e2), where e1 and e2 are small fractions. Therefore, the target interval for the DLT rate is (0.225, 0.325).

The 3 dosing intervals are associated with 3 different dose-escalation decisions. The underdosing interval corresponds to a dose-escalation (E), overdosing corresponds to a dose de-escalation (D), and proper dosing corresponds to remaining at the current dose (R). Given a dosing and a probability distribution, the unit probability mass (UPM) of that dosing interval is defined as the probability of a patient belonging to that dosing interval divided by the length of the dosing interval. The mTPI design calculates the UPMs for the 3 dosing

intervals, and the one with the largest UPM informs the corresponding dose-finding decision, which is the dose level to be used for future patients. For example, if the under-dosing interval has the largest UPM, the decision will be to escalate, and the next cohort of patients will be treated at the next higher dose level. Ji et al. $(2010)^4$ have demonstrated that the decision based on UPM is optimal in that it minimizes a posterior expected loss (ie, minimizes the chance of making a wrong dosing decision).

9.2.2. Statistical Methods for Determining the MTD

This study contains dose escalation with single agent (Part 1A) in patients with advance or metastatic solid tumor, and a combination dose escalation with enzalutamide in previously treated patients with mCRPC (Part 1B). Part 1A and Part 1B will determine the MTD/RP2D in sequential dose escalation cohorts.

The dose finding process in the current study is designed to establish the MTD defined as the highest dose that yields a target of approximately 27.5% probability of DLT and considers equivalent doses that yield probability of DLT in the interval (Equivalence Interval) of (22.5%, 32.5%). Note provided the DLT rate for cardiac toxicity does not exceed 10%. The 27.5% target was chosen based on safety considerations. The prior distribution of DLT is set as a beta (0.5,0.5) and the threshold probability for early termination and dose exclusion is set to 0.95 as suggested in the original mTPI method (Ji et al., 2010). Similarly, doses with an incidence of DLT, eg, 4 out of 10, or apparently higher than 32.5% cannot be selected as MTD, even though it might be allowed by the mTPI method.

Cohorts of patients could receive doses already tested but a dose that is associated with decision to "dose de-escalate, unacceptable toxicity" cannot be revisited and no more patients should be treated at this dose or higher doses for the remainder of the trial.

The maximum sample size for Part 1A would be approximately N=40 for the monotherapy dose escalation and approximately N=20 for the combination dose escalation, but actual sample size will depend on the underlying dose toxicity profile and variability in actual data realization.

The study will continue accruing until one of the three stopping conditions below is triggered.

- The maximum sample size has been achieved (approximately 40 patients in Part 1A monotherapy dose escalation, approximately 20 patients in Part 1B combination dose escalation, and 10 patients in Part 2A monotherapy dose expansion and 20 patients in Part 2B combination dose expansion);
- 6 12 patients that have been enrolled at a dose level that is predicted to be the MTD per the mTPI method;
- All dose levels explored appear to be overly toxic, and the MTD cannot be determined.

Due to binomial data variability in small samples, DLTs may be observed in a first cohort(s) by chance even when the true Probability (DLT) is fairly low. This could result in the estimated posterior DLT rate to exceed the targeted 27.5% very early in the trial.

The following table shows the probability of escalating to the next dose level for a range of underlying true DLT rates. For example, for a DLT that occurs in 10% of patients, there is a greater than 90% probability of escalating. Conversely, for a DLT that occurs with a rate of 70%, the probability of escalating is 3%. It is assumed that dose escalation occurs with either 0/3 or 1/6 patients with DLTs.

Probability of Escalating Dose

True underlying DLT rate	10%	20%	30%	40%	50%	60%	70%	80%	90%
Probability of escalating dose	0.91	0.71	0.49	0.31	0.17	0.08	0.03	0.009	0.001

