The dose finding process in the current study is designed to establish the MTD defined as the highest dose that yields a target of approximately 27.5% probability of DLT and considers equivalent doses that yield probability of DLT in the interval (Equivalence Interval) of (22.5%, 32.5%), provided the DLT rate for cardiac toxicity does not exceed 10%. The 27.5% target was chosen based on safety considerations. The prior distribution of DLT is set as a beta (0.5, 0.5) and the threshold probability for early termination and dose exclusion is set to 0.95 as suggested in the original mTPI method.⁴ Similarly, doses with an incidence of DLT, eg, 4 out of 10, or apparently higher than 32.5% cannot be selected as MTD, even though it might be allowed by the mTPI method.

Cohorts of patients could receive doses already tested but a dose that is associated with decision to "dose de-escalate, unacceptable toxicity" cannot be revisited and no more patients should be treated at this dose or higher doses for the remainder of the trial.

The maximum sample size for Part 1A is approximately 40 patients for the monotherapy dose escalation, approximately 20 patients for the Part 1B combination escalation, approximately 10 patients for Part 2A monotherapy expansion, and approximately 20 patients for Part 2B combination expansion. Actual sample size will depend on the underlying dose toxicity profile and variability in actual data realization.

SCHEDULE OF ACTIVITIES

The Schedule of Activities table provides an overview of the protocol visits and procedures. Refer to the Assessments section of the protocol for detailed information on each assessment required for compliance with the protocol. The investigator may schedule visits (unplanned visits) in addition to those listed in the Schedule of Activities table in order to conduct evaluations or assessments required to protect the well-being of the patient.

SCHEDULE OF ACTIVITIES PART 1A- Monotherapy Dose Escalation

Protocol Activity	Screening (≤28 days	Active Treatment Phase†- One Cycle = 28 days			days		End of Treatment/ Withdrawal ²⁴	Post-Treatment Follow-Up ²⁵
	prior to	Су	cles 1 &	& 2	Cycle	s 3+		
Visit Identifier	enrollment) ¹	Day	Day	Day	Day	Da		
(Visit Window) ^a		1	7	15	1	y 7		
Informed consent ²	X							
Medical/Oncological history ³	X							
Physical examination ⁴	X						X	
Abbreviated physical examination ⁴		X	X	X	X	X		X
Baseline signs and symptoms ⁵	X	X						
Height	X							
Weight	X	X			X		X	

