3.1.1.4. Standard (mTPI) Escalation Phase

The proposed mTPI method for this protocol includes stopping rules and dose escalation/finding criteria which prevent the target DLT rate to reach ≥33% for determining the MTD. Targeting a DLT rate of 27.5% and an acceptable DLT interval (22.5% to 32.5%) will be utilized in both Parts 1A – Monotherapy Dose Escalation (beginning at Dose Level 5) and 1B – Combination Dose Escalation, and will also be used to monitor the DLTs so as not to cross toxicity boundaries in the expansion of a cohort. At least 3 DLT-evaluable patients will be required for the dose escalation decision based on mTPI beginning at Dose Level 5. Note provided the DLT rate for cardiac toxicity does not exceed 10%. The decision rules use a Beta (1,1) prior.

Table 2. mTPI Dose Decision Rules

DLT	n=1	n=2	n=3	n=4	n=5	n=6	n=7	n=8	n=9	n=10	n=11	n=12
0	Е	Е	Е	Е	Е	Е	Е	Е	Е	Е	Е	Е
1	D	S	S	S	S	S	Е	Е	Е	E	Е	Е
2		DU	D	D	S	S	S	S	S	S	S	Е
3			DU	DU	D	D	S	S	S	S	S	S
4				DU	DU	DU	DU	D	S	S	S	S
5					DU	DU	DU	DU	DU	D	S	S
6						DU	DU	DU	DU	DU	DU	DU
7							DU	DU	DU	DU	DU	DU
8								DU	DU	DU	DU	DU
9									DU	DU	DU	DU
10										DU	DU	DU
11											DU	DU
12												DU

Source: https://udesign.laiyaconsulting.com/

E: Escalate to the next higher dose; S: Stay at the same dose; D: De-escalate to the previous lower dose; DU: De-escalate to the previous lower dose and the current dose will never be used again in the trial.

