3.3. MTD Definition

A DLT rate of 27.5% with an equivalence interval of (22.5%, 32.5%) (note: provided the DLT rate for cardiac toxicity does not exceed 10%) will be utilized to estimate the MTD; patients will be enrolled in dose cohorts of 2-4 patients, and each patient will receive 2 courses of PF-06952229 (7 days on, 7 days off) in a 28 day cycle. Due to the discreteness of the dose levels and in the interest of the safety of patients, the estimated MTD is the highest tested dose level with DLT rate ≤ approximately 32.5%. The dose finding decision will be based on a 1-cycle (28 day) DLT observation period.

At least 6 patients have been accumulated on a dose that can be predicted to be the MTD.

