9.6. Sample Size Determination

9.6.1. Part 1

In Part 1, patients will participate in a dose escalation phase aimed at estimating the MTD. The sample size for this component of the study will vary depending on the number of DLTs observed.

A maximum of 60 patients are expected to be enrolled in the dose escalation safety cohorts in Part 1, including approximately 40 patients for the monotherapy dose escalation and approximately 20 patients for the combination dose escalation. The actual number of patients enrolled will depend on the tolerability of PF-06952229 and the number of dose levels required to identify the MTD/RP2D. It is expected that the dose escalation process can be stopped and MTD declared with approximately 6 to 12 patients at the MTD dose. As for the number of patients treated at each dose, it is expected to be at 1 to 4 patients for the doses actually studied. However, since variable cohort size is allowed, the actual number of patients treated at each dose (including MTD) will vary from 1 to 12 patients.

9.6.2. Part 2

For PF-06952229 single agent expansion in patients with mCRPC, the planned sample size of the expansion cohort is 10 based on clinical consideration.

PF-06952229 single agent in combination with enzalutamide for patients with metastatic castration-resistant prostate cancer (mCRPC), assuming a sample size of 20, and the observed PSA50 response is 60% (12/20), the Bayesian posterior probability to demonstrate that the "True PSA50 response" is greater than 37% is 98.15%. Assuming 80% of the 20 patients have measurable disease and are response evaluable (16 patients evaluable), and the observed ORR is 43.75% (7/16), the Bayesian posterior probability to demonstrate that the "True ORR" is greater than 30% is 86.89%.

All the Bayesian calculations above assume a non-informative Uniform (0,1) prior

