Appendix 2. Detailed Dose Escalation/De-Escalation Scheme for mTPI design

DLT	n=1	n=2	n=3	n=4	n=5	n=6	n=7	n=8	n=9	n=10	n=11	n=12
0	E	E	E	E	E	E	E	E	E	E	E	E
1	D	S	S	S	S	S	Е	Е	Е	Е	Е	E
2		DU	D	D	S	S	S	S	S	S	S	E
3			DU	DU	D	D	S	S	S	S	S	S
4				DU	DU	DU	DU	D	S	S	S	S
5					DU	DU	DU	DU	DU	D	S	S
6						DU	DU	DU	DU	DU	DU	DU
7							DU	DU	DU	DU	DU	DU
8								DU	DU	DU	DU	DU
9									DU	DU	DU	DU
10										DU	DU	DU
11											DU	DU
12												DU

Source: https://udesign.laiyaconsulting.com/.

E: Escalate to the next higher dose; S: Stay at the same dose; D: De-escalate to the previous lower dose; DU: De-escalate to the previous lower dose and the current dose will never be used again in the trial.

Escalation/De-escalation algorithms for total number of patients treated at the current dose level (current and previous cohorts)

- With 2 patients treated at current dose level:
 - 0 DLT -> escalate;
 - 1 DLT -> remain at the same dose;
 - 2 DLTs -> de-escalate and consider current dose as intolerable.
- With 3 patients treated at current dose level:
 - 0 DLT -> escalate;
 - 1 DLT -> remain at the same dose;
 - 2 DLTs -> de-escalate;
 - 3 DLTs -> de-escalate and consider current dose as intolerable.
- With 4 patients treated at current dose level:
 - 0 DLT -> escalate;
 - 1 DLT -> remain at the same dose;

- 2 DLT -> de-escalate;
- 3-4 DLTs -> de-escalate and consider current dose as intolerable.
- With 5 patients treated at current dose level:
 - 0 DLT -> escalate;
 - 1-2 DLTs -> remain at the same dose;
 - 3 DLTs -> de-escalate;
 - 4-5 DLTs -> de-escalate and consider current dose as intolerable.
- With 6 patients treated at current dose level:
 - 0 DLT -> escalate;
 - 1-2 DLT -> remain at the same dose;
 - 3 DLTs -> de-escalate;
 - 4-6 DLTs -> de-escalate and consider current dose as intolerable.
- With 7 patients treated at current dose level:
 - 0-1 DLT -> escalate;
 - 2-3 DLTs -> remain at the same dose;
 - 4-7 DLTs -> de-escalate and consider current dose as intolerable.
- With 8 patients treated at current dose level:
 - 0-1 DLT -> escalate;
 - 2-3 DLTs -> remain at the same dose;
 - 4 DLTs -> de-escalate;
 - 5-8 DLTs -> de-escalate and consider current dose as intolerable.
- With 9 patients treated at current dose level:
 - 0-1 DLT -> escalate;
 - 2-4 DLTs -> remain at the same dose;

- 5-9 DLTs -> de-escalate and consider current dose as intolerable.
- With 10 patients treated at current dose level:
 - 0-1 DLT -> escalate;

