Appendix 10. Additional Clinical Safety Data

The data below are from the Part 1A of the Study C3881001 clinical database as of 19 Jun 2020. These data are preliminary and may change. At that time 27 subjects were reported to have been screened and 20 subjects were shown to have been enrolled. The tumor types enrolled were prostate cancer (11 subjects), pancreatic cancer (3 subjects), colon cancer/colorectal cancer (2 subjects), squamous cell head and neck cancer/squamous cell tongue cancer (2 subjects), breast cancer (1 subject), and mesothelioma (1 subject). One subject each was enrolled in the 20, 40, 80 and 150 mg BID accelerated titration cohorts. Six subjects in the 250 mg BID cohort and 3 patients in the 375 BID mg cohort were enrolled prior to a partial clinical hold implemented in July 2019 when 2 subjects experienced Grade 3 events of hepatic hemorrhage (250 mg BID cohort) and intracranial tumor hemorrhage (375 mg BID cohort). Two additional subjects (1 each) with epistaxis and oral hemorrhage were also reported. Subsequently, study entry criteria were modified to reduce the risks of bleeding in a protocol amendment. As of the 19 Jun 2020 database version, no additional AEs of bleeding episodes have been reported.

One hundred and nineteen AEs were reported in 20 patients. Of the 119 AEs,

- Ninety-one AEs were either Grade 1 or 2 in 17 patients.
- The most frequency reported AEs (≥3 subjects) were nausea or worsening nausea (5 subjects), cough (4 subjects), anorexia (4 subjects), nasal drainage or congestion (4 subjects), nasal congestion or intermittent nasal congestion (4 subjects), abdominal pain, or abdominal/right upper quadrant (RUQ) pain (3 subjects), vomiting (3), anemia, or intermittent anemia (3 subjects), dyspnea (3 subjects), fatigue, or worsening fatigue (3 subjects) and headache (3 subjects). Twenty-five Grade 3 AEs were reported in 14 patients.
 - 3 AEs (anemia, intracranial tumor hemorrhage, and intrahepatic hemorrhage, each in 1 patient) were reported as attributed to PF-06952229 by the investigators. Of note, no additional hemorrhagic events have been reported following the modifications made to study entry criteria.

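### The protocol gives the mTPI dose-escalation rule two different priors, and the two disagree on whether to escalate after 1 DLT in 6 patients

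*Protocol*

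**What the plan says.** **The prior.** Protocol 3.1.1.4, which contains Table 2, states: "The decision rules use a Beta (1,1) prior". Protocol 9.2.2 states: "The prior distribution of DLT is set as a beta (0.5,0.5"). The Protocol Summary and SAP 5.2.2 say the same as 9.2.2.

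**Shared settings.** The target DLT rate is 0.275, the proper-dosing interval is (0.225, 0.325), and the exclusion threshold is 0.95. Protocol 9.2.1 and SAP 5.2.1 make the interval with the largest unit probability mass (UPM) the dosing decision.

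**The decision at 1 DLT in 6.** Table 2 has S (stay). Appendix 2, for 6 patients, has: "1-2 DLT -> remain at the same dose".

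**The escalation probabilities.** Protocol 9.2.2 and SAP 5.2.2 print the same row for true DLT rates of 10% to 90%, under this premise: "It is assumed that dose escalation occurs with either 0/3 or 1/6 patients with DLTs".

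**Cohort size and cap.** Protocol 3.3 says "patients will be enrolled in dose cohorts of 2-4 patients". Protocol 9.6.1 says "the actual number of patients treated at each dose (including MTD) will vary from 1 to 12 patients".

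**The concern.** One mTPI design has one prior, and here the documents name two. The choice would be harmless if both priors gave the same decision grid, but with these settings they do not. The SAP contains neither Table 2 nor a Beta(1,1) prior for DLTs. (Its Uniform(0,1) prior in 5.2.3 concerns Part 2 efficacy.) A statistician programming from SAP 5.2.1 and 5.2.2 would therefore get a different grid from the one in Protocol Table 2. Protocol section 9 also allows the SAP to modify the protocol, so the SAP cannot simply be treated as subordinate.

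DLTs and the MTD are primary in Parts 1A and 1B, and both parts use these rules. The printed probability row is the only operating characteristic given for the escalation, and it rests on a decision at 1/6 that Table 2 does not allow.

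**Working it through.** **Inputs.** Target 0.275 and interval (0.225, 0.325): Protocol 9.2.1. Exclusion if P(p > 0.275 | data) > 0.95: Protocol 9.2.2. Priors Beta(1,1) and Beta(0.5,0.5), from the sections above. With x DLTs in n patients and prior Beta(a,b), the posterior is Beta(a+x, b+n−x). UPM is the posterior probability of an interval divided by its length; the lengths are 0.225, 0.10 and 0.675.

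**1. The published row reproduces.** With q = 1−p, escalating at 0/3 or 1/6 in cohorts of 3 has probability q³ + 3pq²·q³ = q³ + 3pq⁵.

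- p = 0.10: 0.729 + 0.177 = 0.906 (stated 0.91).
- p = 0.30: 0.343 + 0.151 = 0.494 (stated 0.49).
- All nine rates: 0.906, 0.709, 0.494, 0.309, 0.172, 0.082, 0.032, 0.009, 0.001. Every stated value agrees.

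**2. Table 2 reproduces under Beta(1,1) only.** Over n = 1 to 12 there are 90 cells. Beta(1,1) gives 0 mismatches; Beta(0.5,0.5) gives 4. UPMs are under / proper / over:

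| DLTs/n | Beta(1,1) | Decision | Beta(0.5,0.5) | Decision |
|---|---|---|---|---|
| 2/4 | 0.351 / 1.188 / 1.189 | De-escalate | 0.446 / 1.203 / 1.154 | Stay |
| 1/5 | 1.80 / 2.26 / 0.54 | Stay | 2.26 / 1.98 / 0.43 | Escalate |
| 1/6 | 2.18 / 2.30 / 0.41 | Stay | 2.65 / 1.92 / 0.31 | Escalate |
| 2/11 | 2.35 / 2.74 / 0.29 | Stay | 2.71 / 2.36 / 0.23 | Escalate |

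At 1/6 under Beta(1,1) the posterior is Beta(2,6). The interval probabilities 0.4908, 0.2302 and 0.2790, divided by 0.225, 0.10 and 0.675, give 2.18, 2.30 and 0.41. Under Beta(0.5,0.5) the posterior is Beta(1.5,5.5). The probabilities 0.5965, 0.1918 and 0.2117 give 2.65, 1.92 and 0.31. All DU (dose-exclusion) cells are the same under both priors.

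**3. The row belongs to the other grid.** With cohorts of 3 and at most 6 patients, Beta(0.5,0.5) escalates at 0/3 and 1/6 and otherwise does not, so it gives q³ + 3pq⁵ exactly. Table 2 under the same limits escalates only at 0/3, which gives q³.

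**4. Escalation probability under Table 2 as printed**, with de-escalation treated as final:

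| True DLT rate | 10% | 20% | 30% | 40% | 50% |
|---|---|---|---|---|---|
| Published | 0.91 | 0.71 | 0.49 | 0.31 | 0.17 |
| Cohorts of 3, by 6 patients | 0.73 | 0.51 | 0.34 | 0.22 | 0.13 |
| Cohorts of 3, by 9 | 0.86 | 0.61 | 0.40 | 0.24 | 0.13 |
| Cohorts of 3, by 12 | 0.92 | 0.69 | 0.44 | 0.25 | 0.14 |
| 3 then 4 (n = 7) | 0.89 | 0.67 | 0.45 | 0.27 | 0.15 |
| Cohorts of 4, by 12 | 0.90 | 0.65 | 0.38 | 0.19 | 0.08 |

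At 6 patients a further 0.24, 0.34, 0.35, 0.28 and 0.19 are at Stay; escalation has not been refused for them. Allowing return to the dose after de-escalation raises the 12-patient values in cohorts of 3 by at most 1.3 points (0.93, 0.70, 0.45, 0.26, 0.14). No first cohort of 2 is modelled, because Protocol 3.1.1.4 requires at least 3 evaluable patients for a decision.

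**The case against.** The strongest reply is that only Table 2 and Appendix 2 tell anyone what to do at 1/6. They agree with each other, and the prior named beside Table 2 generates it exactly. A safety team reads the grid and does not compute posteriors. Table 2 is also the cautious version, no DU cell changes, no printed number is miscalculated, and MTD selection has a prior-free ceiling of about 32.5% observed DLTs (Protocol 3.3). Much of this stands: a site following Table 2 exposes nobody to extra risk. It does not remove the conflict. The largest-UPM rule is itself the dosing decision in Protocol 9.2.1 and SAP 5.2.1, so it yields an action at 1/6 once a prior is set, and SAP 5.2.2 sets the one that escalates.

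The row may come from an ordinary 3+3 calculation and not from Beta(0.5,0.5); it names no prior. That is possible, but it contradicts Table 2 at 1/6 either way. Beta(0.5,0.5) might also be meant only for the 0.95 exclusion rule. The text does not limit it so, and the row would still conflict.

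The reach is narrow. In cohorts of 3 only 1/6 differs, and 2/4 is nearly a tie under Beta(1,1). The other cells can be reached with the permitted cohorts of 2 to 4.

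Appendix 10 suggests 1/6 is realistic but proves nothing. Six subjects were enrolled at 250 mg BID, one with a Grade 3 hepatic hemorrhage attributed to the drug. Whether that was a first-cycle DLT, and whether all six were evaluable, is not stated. Three patients had already been enrolled at 375 mg BID before the hold.

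**Conclusion.** The concern holds and should be corrected. The protocol contradicts itself, and SAP 5.2.2 contradicts Protocol 3.1.1.4, on the prior for the primary dose-finding rule. The effect is confined to four of 90 cells, all more permissive under Beta(0.5,0.5).

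The published escalation probabilities are arithmetically right for a rule that Table 2 does not follow. How far they mislead depends on cohort size and per-dose cap, neither of which the row states as the trial's own. In cohorts of 3, at true rates of 10% to 50%, the row overstates escalation by 6 patients by 18 to 5 points (0.906 − 0.729 at 10%; 0.172 − 0.125 at 50%). By 12 patients the difference runs from −1.5 points (0.906 − 0.921 at 10%) to +5.6 points (0.309 − 0.254 at 40%). These figures treat de-escalation as final and do not model early stopping once 6 to 12 patients are at a predicted MTD.

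**What to change.** **Preferred.** Keep Table 2 and Appendix 2 as printed. Change the prior to Beta(1,1) in the Protocol Summary, Protocol 9.2.2 and SAP 5.2.2. Replace the probability row in Protocol 9.2.2 and SAP 5.2.2 with values computed from Table 2, and state the cohort size and cap. For cohorts of 3 and a cap of 12, at true DLT rates of 10% to 90%, the values are 0.92, 0.69, 0.44, 0.25, 0.14, 0.07, 0.03, 0.008 and 0.001. Remove the sentence assuming escalation at 1/6. If the sponsor expects another cohort size or cap, use that and say so.

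**Alternative, if Beta(0.5,0.5) is intended.** In Table 2 and Appendix 2 change 1/5, 1/6 and 2/11 to E and 2/4 to S. Correct the prior in 3.1.1.4. Keep the published row, labelled as cohorts of 3 with up to 6 patients.

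**Cost.** Wording and a few lines of code, with no extra patients. The preferred route lowers some stated escalation probabilities; the alternative makes four decisions more permissive.
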